3.5.1.4 Missing data handling and other computational rules

No missing data will be imputed.

3.5.2 Secondary endpoints

Wound image assessments will be slotted into the windows found in section 3.1.

3.5.2.1 Wounds remaining closed at 3 months post-wound closure

Of wounds that healed during the registry, the number and percentage of wounds remaining closed at 3 months post-wound closure will be summarized along with 95% CI.

Any wounds that healed less than 3 months before the end of the registry will be excluded from the analysis.

3.5.2.2 VLU recurrence

Of wounds that healed during the registry, the number and percentage of VLU recurrences will be summarized along with 95% CI.

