## 5.4 Secondary Endpoint(s)

---

- Percent of wounds remaining closed at 3 months ( $\pm 1\text{wk}$ ) post-wound closure date, determined via photograph assessed by Tissue Analytics®; non-healed wounds are not included in percent calculation
- For healed wounds, rate of VLU recurrence collected via phone calls and subject-collected photographs at 6 months ( $\pm 1\text{wk}$ ) and 12 months ( $\pm 1\text{wk}$ ) post-treatment
- Change in pain on NPRS compared to baseline at 12 weeks ( $\pm 1\text{wk}$ ), 6 months ( $\pm 1\text{wk}$ ), 12 months ( $\pm 1\text{wk}$ ) post-treatment
- Change on EQ-5D-5L quality of life assessment compared to baseline at 12 weeks ( $\pm 1\text{wk}$ ) and 12 months ( $\pm 1\text{wk}$ ) post-treatment
- Change in VCSS from Baseline to 12 week ( $\pm 1\text{wk}$ ) and 12 month ( $\pm 1\text{wk}$ ) follow-up
- Number of ulcer free weeks defined as weeks from time of closure (complete epithelialization is recorded) to date of recurrence or last contact if no recurrence (at study completion or withdrawal)

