## 10.4 Secondary Efficacy Analyses

---

The secondary endpoints are:

- Wounds remaining closed at 3 months post-wound closure
- VLU recurrence (at same site) at 6 months and 12 months post-treatment
- Change in pain on NPRS compared to baseline at 12 weeks, 6 months, 12 months post-treatment
- Change on EQ-5D-5L quality of life assessment compared to baseline at 12 weeks and 12 months post-treatment
- Change in VCSS from Baseline to 12 week and 12 month follow-up
- Number of ulcer free weeks

The proportion of wounds remaining closed at 3 months post-wound closure will be presented with frequencies and percentages with 95% CIs based on Clopper-Pearson. Similarly, recurrence at 6 months and 12 months post-treatment will be presented with frequencies and percentages with 95% CIs.

Change from baseline for pain on the NPRS, the index health state based on EQ-5D-5L and VCSS will be presented by summary statistics with 95% CIs.

Summary statistics for the number of ulcer free weeks will be presented along with the distribution of the number of ulcer free weeks (time to recurrence) estimated using the KM method and the 25th percentile, median and 75th percentile will be presented along with 95% CIs.

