1.3 Study endpoints

The primary endpoints of the study are:

- Rate of epithelial migration (mm/week) measured by wound perimeter on photograph
- Wound closure at 12 weeks (± 1 wk) post-treatment
- Time from initial treatment with Varithena® to wound closure

The secondary endpoints of the study are:

- Percent of wounds remaining closed at 3 months (± 1 wk) post-wound closure date, non-healed wounds are not included in percent calculation
- For healed wounds, rate of VLU recurrence (at same site)
- Change in pain on NPRS compared to baseline at 12 weeks (± 1 wk), 6 months (± 1 wk), 12 months (± 1 wk) post-treatment
- Change on Euroqol five dimension five level questionnaire (EQ-5D-5L) quality of life assessment compared to baseline at 12 weeks (± 1 wk) and 12 months (± 1 wk) post-treatment
- Change in Venous Clinical Severity Score (VCSS) from baseline to 12 week (± 1 wk) and 12 month (± 1 wk) follow-up
- Number of ulcer-free weeks defined as weeks from time of closure (complete epithelialization is recorded) to date of recurrence (at same site) or last contact if no recurrence (at study completion or withdrawal)

2 Changes to protocol analysis

The interim analyses were expanded to look at hospitalization and safety information. Please see section 3.8 for further details.

Additional exploratory analyses from the Wound Health Index (WHI) will not be conducted.

NPRS analyses will use data from both the sDCT and the electronic data capture (EDC). The analysis will be summarized by each week through 12 weeks, 6 months and 12 months post-treatment. Additionally, the categories by severity will not be summarized but rather the numerical scale will be summarized and presented in a shift table. Refer to section 3.5.2 for further details.

Sub-group analyses will not be performed. There is not enough data collected for the analyses to be meaningful.

3 Statistical methods and analysis

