3.4 Treatment and other medication and therapies

3.4.1 Study treatment

The following index treatment analyses will be summarized by target wound:

- Total injection sites
- Volume injected above the knee (mL)
- Volume injected below the knee (mL)

The number of patients with additional treatment will be summarized. Additionally, the number of additional treatments will also be summarized by wound along with the following:

- Leg (Right, left)
- For target wound? (Yes, no)

- Duration (days) from date of first treatment to the start of an additional treatment
 - $Duration\ (days) = date\ of\ additional\ Varithena\ treatment - date\ of\ first\ Varithena\ treatment + 1$
- Total injection sites
- Volume injected above the knee (mL)
- Volume injected below the knee (mL)

The number of additional treatments will be further split into the number of additional Varithena treatments and the number of adjunctive treatments. Adjunctive treatments are defined as the volume above the knee and below the knee are both 0 mL.

The following treatment analyses will be summarized by visit time point:

- Post-procedure duplex ultrasound performed (Yes, No)
- Duration between treatment and post-procedure duplex ultrasound
 - $Duration\ (days) = Date\ of\ post-procedure\ duplex\ ultrasound - date\ of\ first\ treatment + 1$
- Occlusion of target/treated vein? (Yes, No, N/A), for those that had a post-procedure duplex
- Compression compliance? (Yes, No)
- Hospitalized for target wound since last contact? (Yes, No)
- If wound previously closed/healed, was there recurrence? (Yes, No, N/A)
- Has previously healed target ulcer reopened? (Yes, No)

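### The SAP's recurrence percentage has no time point, and its image rules discard the photographs that Protocol 5.4 uses for 3-month post-closure status; SAP section 2 lists neither change

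*SAP*

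**What the plan says.** **Recurrence.** Protocol 5.4 defines the endpoint for healed wounds as "rate of VLU recurrence collected via phone calls and subject-collected photographs at 6 months" and also at 12 months post-treatment. Protocol 10.4 gives the analysis: "recurrence at 6 months and 12 months post-treatment will be presented with frequencies and percentages with 95% CIs". SAP 1.3 shortens the endpoint to "For healed wounds, rate of VLU recurrence (at same site", and SAP 3.5.2.2 analyses it as follows: "Of wounds that healed during the registry, the number and percentage of VLU recurrences will be summarized along with 95% CI". Neither SAP section names a time.

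Recurrence appears in two other places in the SAP. Section 3.4.1 tabulates two answers by visit: "If wound previously closed/healed, was there recurrence? (Yes, No, N/A" and "Has previously healed target ulcer reopened? (Yes, No". Section 3.5.2.6 plans a Kaplan-Meier analysis of time from closure to recurrence and takes recurrence from the EDC.

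**Status at 3 months after closure.** Protocol 5.4 has this "determined via photograph assessed by Tissue Analytics®; non-healed wounds are not included in percent calculation". SAP 1.3 keeps the endpoint but not the photograph clause; it reads "post-wound closure date, non-healed wounds are not included in percent calculation". Under Protocol 8.1.6 and 8.2.7 the subject takes this photograph with the sDCT. SAP 4.3 step 2 discards sDCT photographs dated later than the closure date the site entered in the EDC.

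**Disclosure.** SAP section 2 lists four changes to the protocol analysis: the interim analysis, the Wound Health Index, the NPRS and the sub-groups.

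**The concern.** Recurrence rate is part of the stated objective in Protocol 5.1 and SAP 1.2. An untimed percentage pools wounds with unequal follow-up after closure and cannot be read as a 6-month result. An analyst who wants the 6-month figure has to choose its definition from a table filed under study treatment.

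The image rule is a separate problem. A photograph taken 3 months after closure is by construction a post-closure photograph, so the rule removes the data source that the protocol names for that endpoint. A photograph that shows a reopened ulcer is removed along with the rest. The percentage remaining closed would then come from the site's entry, with no planned comparison against the image.

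Both are changes to secondary endpoints, and a reader who relied on SAP section 2 would not learn of either.

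**Working it through.** The documents state no figure for this point, so there is nothing to reproduce. The check sets the texts side by side and then counts days.

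**Step 1. Compare the endpoints.**

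| Item | Protocol | SAP |
|---|---|---|
| Recurrence times | 6 and 12 months post-treatment (5.4, 10.4) | none (1.3, 3.5.2.2) |
| Recurrence source | calls and subject photographs (5.4) | EDC (3.5.2.6) |
| 3-month post-closure source | centrally assessed photograph (5.4) | not named (1.3, 3.5.2.1); later sDCT photographs removed (4.3 step 2) |
| Listed in SAP section 2 | – | no |

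In the same SAP 1.3 list, the NPRS, EQ-5D-5L and VCSS endpoints keep their times. Section 2 does record a change of source and timing for the NPRS, so changes of this kind are ones the SAP normally discloses.

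**Step 2. What the untimed percentage estimates.** Follow-up ends at about 12 months. Any recurrence among wounds that healed during the registry is therefore close to the 12-month figure, apart from dropout. It is not the 6-month figure, because it counts later recurrences and includes wounds that healed after month 6.

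**Step 3. Whether another SAP analysis supplies the 6-month figure.**

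- The first item in SAP 3.4.1 is conditional on earlier healing and has a not-applicable answer, so Yes plus No largely gives a denominator. The general Clopper-Pearson rule in SAP 3.1 could supply the interval. However, two overlapping items are tabulated and neither is named as the endpoint. The hospitalization item beside them is worded as since the last contact; the recurrence items do not say whether they are cumulative.
- The Kaplan-Meier analysis in SAP 3.5.2.6 handles unequal follow-up, but it counts from closure rather than treatment and tabulates weekly rates only through 12 weeks.

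**Step 4. What step 2 of SAP 4.3 removes.** If the 3 months are counted from the site-recorded closure date, every 3-month post-closure sDCT photograph is dated after that date, so all are removed. For wounds healed before the 6-month call, the 6-month sDCT photograph goes too. Photographs that the investigator takes at Week 12 or Month 12 may survive, because section 4.3 covers sDCT data only.

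**Step 5. Whether lifting step 2 would be enough.** SAP 3.5.2 slots images into the SAP 3.1 windows. These count from treatment and cover days up to 98, 153–213 and 335–395; images outside them are not summarized. Let C be the closure day on the SAP scale and take 3 months as 91 days (an assumption). The photograph falls on day C + 91.

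- Closure days that leave 91 days before day 365: 365 − 91 = 274.
- C + 91 between 99 and 152 gives C = 8–61, which is 54 days.
- C + 91 between 214 and 334 gives C = 123–243, which is 121 days.
- In no window: 54 + 121 = 175 of 274 days (64%).
- At the ends of the ±1 week allowance: 175 of 365 − 84 = 281 days (62%) and 175 of 365 − 98 = 267 days (66%).

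For the other 274 − 175 = 99 closure days the image would be labelled 12 weeks, 6 months or 12 months post-treatment. No window identifies it as the 3-month post-closure image. These are counts of days, not of wounds.

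**The case against.** The strongest reply is that the SAP, read as a whole, still delivers most of this. The by-visit item is conditional on healing, and together with the Clopper-Pearson rule it can reasonably yield 6- and 12-month percentages with intervals. Its exact meaning may be settled in the eCRF or the table shells, which are separate documents and were not seen. The Kaplan-Meier analysis deals with censoring. The photograph clause is in Protocol 5.4 but not in the synopsis or in 10.4, and Protocol 8.1.6 has a telephone assessment alongside the photograph. The SAP cites protocol version 1.1, and the version of the protocol supplied cannot be confirmed. The registry is descriptive and tests no hypothesis.

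Much of this stands, and it rules out three stronger readings that a reader might infer.

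- **That 6-month recurrence will not be reported.** The by-visit table may report it. What is missing is a statement that this is the endpoint and how its answers accumulate.
- **That 3-month closed status cannot be computed, or rests only on what the subject says by telephone.** SAP 3.5.2.1 still analyses it. Protocol 8.2.7 lets the investigator view all photographs, so the site's entry may reflect the image.
- **That nothing accounts for unequal follow-up.** The Kaplan-Meier analysis does, from closure.

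It may also be said that step 2 was meant only for the perimeter data. That is plausible, but nothing in SAP 4.3 limits it, and the section describes the compiled data as being for the analyses generally. The reply does not restore the two time points to SAP 3.5.2.2, retain the photographs, or put either change in section 2.

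**Conclusion.** The point holds in two parts. First, SAP 1.3 and 3.5.2.2 no longer specify recurrence at 6 and 12 months. The 12-month figure is roughly preserved, and the 6-month figure depends on how a by-visit table is read. Second, SAP 4.3 step 2 removes all 3-month post-closure sDCT photographs, so that endpoint is not computed as Protocol 5.4 defines it, and no reconciliation of photograph and site entry is specified. SAP section 2 lists neither change.

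The size that follows from the SAP as written is the complete removal of those photographs. This assumes that the 3 months run from the site-recorded closure date. The count of 175 of 274 closure days assumes 91 days and follow-up to day 365. It describes what would happen if step 2 alone were lifted, and it serves only to show that a further window is needed. The documents do not allow an estimate of how many wounds would be misclassified or how far either percentage would move.

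The comparison is with the protocol text supplied, without sight of the eCRF or the table shells. The endpoints are secondary, so this should be corrected, but it does not affect the primary endpoints.

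**What to change.** 1. In SAP 3.5.2.2, report recurrence at 6 and at 12 months post-treatment, each cumulative since closure, with a Clopper-Pearson 95% CI. Use wounds healed by that time as the denominator, and show how many of them had no contact at that time.
2. Limit SAP 4.3 step 2 to the wound-perimeter analysis. Keep post-closure photographs for 3-month status and for recurrence.
3. Add to SAP 3.1 a window of 3 months ±1 week counted from the closure date.
4. List wounds for which the photograph and the EDC entry disagree.
5. Record in SAP section 2 any departure that is kept, such as the EDC as sole source, with the reason.

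The cost is SAP wording, one window, one extra recurrence row and one listing. The protocol already requests the photographs and the call assessments, so no new data collection is needed.

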### 7.1.4 Duration of Treatment and Follow-up

Following the initial treatment with Varithena®, each subject is followed for 12 months. Additional treatment can be administered following the initial treatment; however, it is recommended that re-treatment occur as close to the time of the initial treatment as is possible, but not sooner than 5 days, according to FPI and IFU. Date of re-treatment, number of injection sites, and volume above and below the knee is recorded in the iDCT.

During the follow-up period, subjects are followed for VLU-related hospitalizations, wound recurrence, and other clinical outcomes. Subjects are assessed at the investigational site at Week 1 Follow-up visit (about one week after treatment), 12 weeks ( $\pm 1$  wk) post-treatment and 12 months ( $\pm 1$  wk) post-treatment. Subjects are contacted by telephone for follow-up 3 months ( $\pm 1$  wk) post wound-closure, and 6 months ( $\pm 1$  wk) post-treatment. Subjects collect wound photographs between follow-up visits when the wound dressing is being changed at the WCC.

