#### **8.1.4 Week 2 through Wound Closure (at WCC)**

---

The subject does not return to the investigational site at this time. The subject presents to a WCC for wound care and dressing changes on about a weekly basis. During each visit to the WCC, subject is asked to take a photograph (multiple photographs for circumferential wounds) of the wound and answer the NPRS question using the sDCT. It is important that the subject understands that the WCC staff may not be aware of the registry, so collection of the photograph(s) and answering the NPRS question should be completed independently. The subject should refer questions about the sDCT and data collection to the investigational site, or contact Tissue Analytics® for technical support.

If the wound is not healed at the Week 12 Follow-up visit, subject continues to collect photograph(s) and answer NPRS questions at weekly WCC visits until wound closure.

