3.5.2.6 Number of ulcer free weeks (time to recurrence)

The number of ulcer free weeks (time between healed wound and recurrence) will be summarized by mean, median, standard deviation, quartiles, minimum and maximum. If a patient's wound healed but did not have a recurrence, the patient will be censored at the last date of study. Additionally, the distribution of the time to recurrence will be analyzed by KM methodology. The 25th percentile, median and the 75th percentile will be presented along with the 95% CIs using the methodology of Brookmeyer and Crowley (1982)² using the log-log standard error. KM rates will be presented for each week through 12 weeks with the corresponding 95% CIs using the log-log transformation methodology of Kalbfleisch and Prentice (1980)³. Plots of the KM curve will also be provided.

Information for recurrence will be based on data from the EDC.

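### SAP 3.5.2.2 gives recurrence as a crude percentage of all healed wounds despite unequal time at risk, and the censored analysis in 3.5.2.6 tabulates rates only to 12 weeks after closure

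*SAP*

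**What the plan says.** - **Follow-up clock.** Protocol 7.1.4: "Following the initial treatment with Varithena®, each subject is followed for 12 months".
- **Late closure counts.** For a wound still open at Week 12, Protocol 8.1.4 says the "subject continues to collect photograph(s) and answer NPRS questions at weekly WCC visits until wound closure".
- **Protocol endpoint.** Protocol 5.4: "For healed wounds, rate of VLU recurrence collected via phone calls and subject-collected photographs at 6 months", and again at 12 months, both counted from treatment. Protocol 10.4 presents these as frequencies and percentages with intervals.
- **SAP analysis of recurrence (3.5.2.2).** "Of wounds that healed during the registry, the number and percentage of VLU recurrences will be summarized along with 95% CI". That sentence is the whole section.
- **Neighbouring durability endpoint (SAP 3.5.2.1).** "Any wounds that healed less than 3 months before the end of the registry will be excluded from the analysis".
- **Missing data (SAP 3.5.1.4).** "No missing data will be imputed". No rule covers a healed wound whose patient leaves before recurrence is assessed.
- **Ulcer-free weeks (SAP 3.5.2.6).** "If a patient's wound healed but did not have a recurrence, the patient will be censored at the last date of study". The KM method supplies quartiles and a plot, and "KM rates will be presented for each week through 12 weeks with the corresponding 95% CIs".

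**The concern.** A wound can recur only after it has closed. Time at risk is therefore 12 months minus time to closure, and less for anyone who withdraws or is lost. The 3.5.2.2 percentage gives equal weight to a wound closing at week 6 (46 weeks at risk) and one closing at month 11 (about 4 weeks). The result then reflects how fast wounds closed and how long patients stayed, as well as how durable closure was. Slower healing or more dropout lowers reported recurrence, which is the direction that flatters the product.

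Recurrence rate is a stated objective of the registry. Protocol 4.1 cites 12-month recurrence of 12% and 28% from a randomised trial of surgery plus compression against compression alone, and readers are likely to set the registry's figure beside these.

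**Working it through.** The plan states no expected recurrence rate, so there is no figure of its own to reproduce. The check asks what the crude percentage would show for a known risk from closure.

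**Inputs**
- Follow-up: 52 weeks from treatment (Protocol 7.1.4).
- True 12-month recurrence risk from closure, R: 12% and 28%. These are the Protocol 4.1 figures, assumed here to run from closure.
- Share closed by week 12, p: 62% and 92%, the control and foam arms of a small trial in Protocol 4.1 (13/21 and 12/13), and 40% as an assumed slow case. For orientation, if healing is exponential, the cited mean of 142 days implies 1 − e^(−84/142) = 45% by week 12, and the cited median of 54 days implies 1 − 0.5^(84/54) = 66%.
- Loss after closure: not stated; assumed 0% or 20% per year.
- Exponential closure, constant recurrence hazard, and loss unrelated to recurrence: all assumed.

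**One wound.** If it closes at month m and is followed to month 12, the chance of an observed recurrence is 1 − (1 − R)^((12 − m)/12). At R = 28%, closure at month 3, 6, 9 or 11 gives 21.8%, 15.1%, 7.9% or 2.7%.

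**All healed wounds.** Let a = −ln(1 − p)/12, h = −ln(1 − R)/52, d = −ln(1 − loss)/52 and k = h + d. Then

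crude = (h/k) × {1 − a[e^(−52k) − e^(−52a)] / [(a − k)(1 − e^(−52a))]}.

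Example with p = 40%, R = 28%, no loss: a = 0.04257, h = k = 0.006317, e^(−52k) = 0.72, e^(−52a) = 0.109. Crude = 1 − (0.04257 × 0.611)/(0.03625 × 0.891) = 19.5%.

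| Closed by week 12 | Yearly loss | True 28% shown as | Relative shortfall | True 12% shown as | Relative shortfall |
|---|---|---|---|---|---|
| 40% | 0% | 19.5% | 30.4% | 8.2% | 31.9% |
| 40% | 20% | 18.0% | 35.7% | 7.5% | 37.3% |
| 62% | 0% | 22.3% | 20.2% | 9.4% | 21.5% |
| 62% | 20% | 20.5% | 26.8% | 8.6% | 28.2% |
| 92% | 0% | 25.8% | 8.0% | 11.0% | 8.7% |
| 92% | 20% | 23.4% | 16.3% | 9.9% | 17.2% |

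(Shortfalls are computed before rounding.) Mean time at risk without loss is about 35, 40 and 47 weeks in the three healing cases.

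**Early exits alone.** Comparing each pair of rows isolates loss to follow-up: 18.0/19.5, 20.5/22.3 and 23.4/25.8 are each about 8% to 9% below 1. On the protocol's treatment clock, this is the only bias.

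**Can the interval miss the truth?** With mean healing of 142 days, R = 28% and no dropout, simulation has 185 of 200 wounds heal and 37 recur. The Clopper-Pearson interval for 37/185 is 14.5% to 26.5%, which excludes 28%.

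**Does 3.5.2.6 fill the gap?** In the simulation, KM from closure recovers the true risk: 15.1% at 182 days against a true 15.1%, and 23.6% to 23.7% at 300 days against 23.7%. But the last tabulated rate is at 12 weeks, where the true value is only 7.3%. Under a constant hazard at R = 28%, the 25th percentile falls at 365 × ln(4/3)/(−ln 0.72) = day 320 after closure. Only wounds closed within 365 − 320 = 45 days of treatment are followed that long. The median falls at day 770. At R = 12% the two fall at days 821 and 1,979. The planned quartiles would thus be mostly or wholly unestimable.

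**The case against.** The strongest reply is that most of the remedy is already planned. SAP 3.5.2.6 handles unequal follow-up by censoring, from closure, with quartiles, weekly rates and a plot, and Protocol 10.4 plans KM as well. SAP 3.4.1 also summarises recurrence by visit, with a not-applicable category. A reader of 3.5.2.2 alone might infer that the plan has no censored recurrence analysis, and that would be wrong. What remains is that no KM rate beyond 12 weeks is tabulated and 3.5.2.2 does not point to 3.5.2.6.

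Four further objections also limit the point:

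- **The benchmark is a different quantity.** For recurrence by 12 months after treatment, short exposure in late healers is part of the definition. It would be too strong to say that late healing biases the protocol's own endpoint. SAP 3.5.2.2, however, drops the time points, so its figure is tied to neither clock.
- **The handling of early exits is inferred.** No passage says that lost patients count as recurrence-free. It follows from a denominator of all healed wounds with no exclusion or censoring rule.
- **The registry's end in 3.5.2.1 is ambiguous.** With about 12 months of enrolment, a study-level date would keep a wound closed in a patient's month 11, with no 3-month check left. But the protocol synopsis (Duration) and Protocol 6.3 also use the term per subject, and read that way the wound is excluded. The documents do not establish an error here.
- **The stakes are moderate.** This is a descriptive secondary endpoint with no hypothesis. No comparison with the cited 12% and 28% is planned, and Protocol 4.1 does not say from when those rates are counted.

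**Conclusion.** The point holds in a limited form. Read as a measure of how durable closure is over a year, the 3.5.2.2 percentage is too low by about 8% to 36% in relative terms when the true risk is 28%, and by about 9% to 37% when it is 12%. The low end needs healing as fast as the 92% foam arm of 13 patients and no dropout. The high end needs 40% closed by week 12, for which the documents give no source, and 20% yearly loss. The size rests on those assumptions together with exponential healing and a constant hazard. The direction holds for any positive recurrence hazard after closure.

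On the protocol's treatment clock the bias comes from early exits alone, about 8% to 9% at the assumed 20% loss. Because 3.5.2.6 stops its rates at 12 weeks, no longer-term recurrence rate that allows for unequal follow-up would be tabulated. This should be changed, but it is a gap in reporting rather than the absence of a suitable method.

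**What to change.** 1. **SAP 3.5.2.6:** extend the KM table to later times since closure that follow-up supports, for example 26 and 39 weeks, with numbers at risk. Censor at the last contact at which the wound area was assessed.
2. **SAP 3.5.2.2:** cross-reference that table as the main recurrence estimate. Keep the crude count as supportive, with person-weeks at risk beside it.
3. **SAP 3.5.2.1:** state that the registry's end means the patient's own end of follow-up, and report the 13-week KM estimate alongside the percentage so that early exits are censored.

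The cost is SAP wording and a few table rows, with no new data. Reported recurrence will be somewhat higher and its interval slightly wider. One limit remains: KM assumes that censoring is unrelated to recurrence risk. Only wounds closed by week 52 − 39 = 13 can be followed for 39 weeks, so if slow healers recur more often, the late estimate leans on the fast healers. The numbers at risk will show how far.
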